### **9.2 Handling of Missing and Incomplete Data**

Subjects may have missing specific data points for a variety of causes. In general, data may be missing due to a subject's early withdrawal from study, a missed visit, or non-evaluability of a specific clinical measurement at its planned clinical visit. Unless specified, no imputation will be used. The general procedures outlined below describe what will be done when a data point is missing.

#### **9.2.1 Genant Semiquantitative Grades**

Missing semiquantitative grades will not be imputed to determine vertebral fracture status.

#### **9.2.2 Vertebral Fracture Assessment**

Because in an adult, a vertebral fracture can only get worse or at best remain at the same severity over time, the Genant semiquantitative grade for a vertebra can only increase or remain the same. In other words, once a vertebral fracture is identified, the subsequent spinal radiographs will always show fracture. Therefore, any missing post-baseline vertebral fracture status due to missing spinal x-ray assessment will be imputed using the status from the last nonmissing post-baseline visit (ie, last observation carried forward [LOCF]).

### **9.2.3 DXA or QCT Endpoints**

Missing baseline values for endpoints by DXA or QCT at any anatomical site will not be imputed. Missing post-baseline values will be imputed using LOCF approach (by carrying forward the last nonmissing post-baseline value prior to the missing value from the same anatomical site). For the open-label period endpoints, only the open-label period value will be used for imputation, the values in the double-blind period will not be carried forward into open-label period. The LOCF imputation will be done up to Month 36. Missing post-baseline data will not be imputed when repeated measures model is employed as a sensitivity analysis.

If a subject has values from different DXA machine types (ie, Hologic and Lunar) or QCT machine types only those values that are collected from the same machine type as the baseline will be used for analyses and imputation. For anatomical sites that can be measured on different body sides (ie, left and right), only those values that are collected from the same body side as the baseline will be used for analyses and imputation.

### **9.2.4 Bone Turnover Markers/Biomarkers and PK**

Missing bone turnover maker or biomarkers (either baseline or post-baseline values) or PK will not be imputed. Any values below the lower limit of quantification will be imputed using the lower limit of quantification for analysis.

### **9.2.5 PRO Measurements**

#### **9.2.5.1 OPAQ-SV**

Missing baseline or post-baseline OPAQ scores will not be imputed.

#### **9.2.5.2 EQ-5D-5L**

Missing baseline or post-baseline EQ-5D-5L scores will not be imputed.

#### **9.2.5.3 BPI Worst Pain**

Missing baseline or post-baseline BPI worst pain score will not be imputed.

#### **9.2.5.4 LAD**

Subjects answering “no” to cutting down on things (Question 1) will be assigned 0 day of cutting down on things for Questions 2a (due to health reasons) and 2b (due to a fracture if a fracture is reported before the PRO assessment). For subjects answering

“subject does not know” to cut down on things (Question 1), the missing days of cutting down on things will not be imputed. For subjects answering “yes” to cut down on things (Question 1) but not knowing the number of days cutting down on things in Question 2a or Question 2b, the missing days of cutting down on things will not be imputed. Days of cutting down on things will not be imputed if the question is not answered at all.

Similarly, subjects answering “no” to hospitalization overnight (Question 3) will be assigned 0 day of hospitalization overnight for Question 3a (due to health reasons) and 3b (due to a fracture if a fracture is reported before the PRO assessment). For subjects answering “yes” to hospitalization overnight (Question 3) but not knowing the number of days of hospitalization overnight, the missing days will not be imputed. For subjects answering “subject does not know” to hospitalization overnight (Question 3), the missing days will not be imputed. Days of hospitalization overnight will not be imputed if the question is not answered at all. Similar approach will be applied to days of stay in bed (Question 4).

If the reported days of cutting down on things, hospitalization overnight, or stay in bed are greater than the recall period (30 days), minimum (30, reported days) will be applied to baseline and post-baseline visit.

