##### **Pre-fracture Baseline for PRO/ClinRO Endpoints**

Pre-fracture baseline for PRO/ClinRO endpoints is the closest recorded PRO/ClinRO measurements before the visit of reporting a nonvertebral fracture or clinical vertebral fracture.

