## **7.7 Analysis Set for Post Fracture PRO/ClinRO Endpoints**

This analysis set includes all randomized subjects who experienced a nonvertebral or clinical vertebral fracture in the double-blind period and have a pre-fracture baseline and  $\geq 1$  post fracture evaluation at or before the time point under consideration. Note that this subset could potentially be different from endpoint to endpoint due to missing data. Subjects in this subset will be analyzed according to the randomized treatment assignment.

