### **LAD Questionnaire**

The number and percent of subjects reporting in the past month cutting down on things due to health reasons (Question 1), in hospital overnight due to health reasons (Question 3), and stay in bed due to health reasons (Question 4) at months 6, 12, 18, 24, 30, and 36, and at month 1, 2 and 3 after fracture will be summarized descriptively. Subjects reporting cutting down things but with missing value for number of days will not be included in the respective analysis of number of days.

Number of days in the past month of cutting down things due to health reasons (Question 2a), in hospital overnight due to health reasons (Question 3a), and stay in bed due to health reasons (Question 4a) at months 6, 12, 18, 24, 30, and 36 will be summarized descriptively. The treatment comparison at months 6, 12, 18, and 24, will be done using the repeated measures model adjusted for age strata, presence or absence of severe vertebral fracture at baseline, treatment, visit, treatment by visit interaction, and baseline.

Number of days in the past month of cutting down on things due to a fracture (Question 2b), in hospital overnight due to a fracture (Question 3b), and stay in bed due to a fracture (Question 4b) at month 1, month 2 and month 3 after fracture will be summarized descriptively in subjects who have a fracture during the 12-month double-blind period. The treatment comparison will be done using the repeated

measures model adjusted for age strata, presence or absence of severe vertebral fracture at baseline, treatment, visit, treatment by visit interaction, fracture type, pre-fracture baseline and change from pre-fracture baseline at report of fracture.

Change from pre-fracture baseline in number of days in the past month of cutting down things due to health reasons, in hospital overnight due to health reasons, and stay in bed due to health reasons at month 1, month 2 and month 3 after fracture and each first post fracture visit will be summarized descriptively in subjects who have a fracture during the 12-month double-blind period. The treatment comparison will be done using the repeated measures model adjusted for age strata, presence or absence of severe vertebral fracture at baseline, treatment, visit, fracture type, pre-fracture baseline, change from pre-fracture baseline at report of fracture and treatment by visit interaction.

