Change from pre-fracture baseline in number of days in the past month of cutting down things due to a fracture, in hospital overnight due to a fracture, and stay in bed due to a fracture at fracture reporting visit and each first post fracture visit will be summarized descriptively in subjects who have a fracture during the 12-month double-blind period. The treatment comparison will be done using the repeated measures model adjusted for age strata, presence or absence of severe vertebral fracture at baseline, treatment, visit, fracture type, pre-fracture baseline, change from pre-fracture baseline at report of fracture and treatment by visit interaction.

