### 13.3.3 LAD Questionnaire

Limited activity days questionnaire evaluate subjects' back pain experience during the past 30 days and this questionnaire has been used in several clinical trials including the Fracture Intervention Trial (Nevitt MC, 2000). The responses of each question will be analyzed separately. The responses of each question are as follows:

[figure not shown]
Questions	Responses
1, 2a, 2b	If question 1 = 'Yes', then answer question 2a and 2b.  2a = Specify number of days cutting down on things due to health reasons or mark 'Don't know'  2b = Specify number of days cutting down on things due to a fracture  If question 1 = 'No' or 'Subject does not know', then answer question 3a.
3a, 3b	If question 3a = 'Yes', then specify number of nights spent in a hospital due to health reasons and then answer question 3b.  3b = Specify number of nights spent in a hospital due to a fracture.  If question 3a = 'No' or 'Subject does not know', then answer question 4a.
4a, 4b	If question 4a = 'Yes', then specify number of days staying in bed for more than half the day (NOT in a hospital) more than half of the day due to health reasons and then answer question 4b.  4b = Specify number of days spent in bed for more than half the day due to a fracture.  If question 4a = 'No' or 'Subject does not know', then questionnaire is complete.

The responses of each question will be analyzed individually.

[figure not shown]

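### The LAD zero-assignment rule leaves the pre-fracture 'due to a fracture' items missing for women who were unlimited before a first on-study fracture, so the exploratory change-from-pre-fracture comparison of those items loses them selectively

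*SAP*

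**What the plan says.** **Skip pattern.** SAP 13.3.3 routes a woman without limitation past the day counts: "If question 1 = 'No' or 'Subject does not know', then answer question 3a". She never reaches 2a or 2b. The hospital and bed-rest questions skip in the same way.

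**Zero rule.** SAP 9.2.5.4 then assigns 0 on a No answer. For the health-reasons items this is unconditional. For the fracture-attributed items it is conditional: "and 2b (due to a fracture if a fracture is reported before the PRO assessment" and, for hospital nights, "3b (due to a fracture if a fracture is reported before the PRO assessment". Question 4 is handled by a similar approach.

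**Pre-fracture baseline.** SAP 6.1.1 defines it as the "closest recorded PRO/ClinRO measurements before the visit of reporting a nonvertebral fracture or clinical vertebral fracture".

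**Models.** In the LAD part of SAP 10.5.4, the third paragraph models fracture-attributed days at Months 1 to 3 after fracture. Its adjustment terms include "fracture type, pre-fracture baseline and change from pre-fracture baseline at report of fracture". The last paragraph analyses "Change from pre-fracture baseline in number of days in the past month of cutting down things due to a fracture", and likewise for hospital nights and bed days. It names the fracture reporting visit and the first post-fracture visit, and its model includes visit, treatment by visit, and the change at report of fracture.

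**Analysis set.** SAP 7.7 takes women who "experienced a nonvertebral or clinical vertebral fracture in the double-blind period and have a pre-fracture baseline and" at least one post-fracture evaluation, and allows the set to differ by endpoint because of missing data.

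**The concern.** The condition in the zero rule concerns whether a fracture was reported before the assessment, and a pre-fracture assessment comes before the report by definition. For a first on-study fracture the condition therefore fails at exactly the assessment that the change analysis needs. A woman who reported no limitation of any kind had 0 fracture-attributed days, yet the SAP leaves her value blank.

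The loss is selective. The women kept are mainly those already limiting activity, in hospital or in bed before the fracture, for whatever reason, plus those with an earlier reported on-study fracture. A treatment comparison in that subset describes a different population from all women who fractured.

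The second difficulty is in the last LAD paragraph. If the reporting visit is one of the modelled outcomes, the change at that visit stands on both sides of the equation.

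**Working it through.** The plan states no figure on this point, so the main check is a trace through the text.

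**Trace for a first on-study fracture, parent answer No beforehand**

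1. Item 2b is skipped (13.3.3), so it has no recorded value.
2. The zero rule does not apply, because no on-study fracture had been reported (9.2.5.4). Going back to an earlier assessment does not help, since that also precedes the report. SAP 13.1.1.11 dates the pre-fracture baseline from the fracture itself rather than from the reporting visit, with the same result.
3. No other rule fills the gap. SAP 9.2 imputes nothing unless specified, and 9.2.5.4 does not impute unanswered day counts. The multiple imputation in 10.5.4 covers OPAQ-SV, EQ-5D-5L VAS and BPI scores at report of fracture; it does not cover LAD.
4. Change from pre-fracture baseline in 2b therefore cannot be computed. A covariate missing for a woman also removes all her rows from a repeated measures model.
5. At and after the reporting visit the condition is met, so a No then gives 0. Only the pre-fracture value is affected. The trace applies item by item: 1 to 2b, 3 to 3b, 4 to 4b.

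**Scale**

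Inputs are from SAP 3.2: 2,000 women per arm; ALN nonvertebral rate about 4% a year (or 5.5% × 0.75 = 4.125%); 27% reduction; new vertebral rate 2.2% a year on ALN, halved on romosozumab; one third of new vertebral fractures clinical; 10% first-year dropout.

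With clinical fracture rate r and dropout rate d = −ln(0.9) = 0.1054, the expected proportion with a first event in 12 months is r/(r+d) × [1 − exp(−(r+d))].

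- ALN: r = 0.04 + 0.022/3 = 0.0473, giving 2,000 × 0.0439 = 87.8 women.
- Romosozumab: r = 0.04 × 0.73 + 0.011/3 = 0.0329, giving 2,000 × 0.0307 = 61.4 women.
- Total 149.2. With 4.125% in place of 4%, the total is 153.1.

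The share answering No before the fracture is not in the documents. As an assumption, applied to 149.2 women:

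| Share answering No | Women lost | Women kept |
|---|---|---|
| 30% | 45 | 104 |
| 50% | 75 | 75 |
| 70% | 104 | 45 |
| 90% | 134 | 15 |

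With 153.1 women, the losses are 46, 77, 107 and 138. The table ignores women with an earlier on-study fracture, who do get 0.

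**Outcome as its own covariate**

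Let D₀ be the change at the reporting visit. At that visit the model reads D₀ = μ₀ + τ₀·treatment + β·D₀ + other terms + error. With β = 1 and every other term 0, the residual is exactly 0. Under the unstructured covariance of SAP 10.5.1.6, the variance at that visit can then collapse to 0 and τ₀ goes to 0. Under a substitute structure that yields some other β, rearranging gives τ₀ = (1 − β) × the adjusted treatment difference in D₀. Neither quantity is a treatment effect that a reader could interpret.

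**The case against.** Several points on the other side are fair.

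- **Meaning of a reported fracture.** SAP 9.2.5.4 does not say on-study. Eligibility requires a prior vertebral or proximal femur fracture, so if pre-study fractures count, the condition would usually be met. This stands as an ambiguity. The LAD fracture analyses in 10.5.4 are restricted to women who fracture in the double-blind period, which makes the on-study reading the natural one.
- **Which baseline item.** The third LAD paragraph does not name the item behind its pre-fracture baseline. If the health-reasons item is meant, women stay in that model. This stands. The last paragraph is different, because its outcome is change in the fracture item itself.
- **Which visits are modelled.** The last paragraph attaches the two visits to the descriptive summary and does not say outright which enter the model. This also stands, so the self-covariate point is conditional. A treatment-by-visit model needs visits, however, and the reporting visit is one of only two listed.
- **What cannot be seen.** The LAD form is not reproduced and the code is redacted. The programs may already set these values to 0, but the SAP text does not authorise that.

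A reader might infer that the burden-of-fracture objective cannot be answered. The documents do not support this. The objective in SAP 2.3 is descriptive and uses four instruments. The OPAQ-SV, EQ-5D-5L and BPI analyses do not use the LAD rule, the health-reasons items receive 0 unconditionally, and fracture-attributed days after fracture are also summarised descriptively. SAP 10.5.4 itself warns that post-fracture treatment comparisons are not protected by randomization.

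**Conclusion.** The concern holds in a narrow form. On the on-study reading, the zero rule discards a value known to be 0, and the analysis of change from pre-fracture baseline in fracture-attributed days loses women who were unlimited before a first on-study fracture. The Months 1 to 3 model of fracture-attributed days is affected only if its baseline is the same item. The size rests on an assumed share of 30% to 90%, or about 45 to 135 of roughly 150 women; no narrower range can be supported from the documents.

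If the reporting visit is a modelled outcome, its treatment contrast is not interpretable, however the zero rule is read.

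The importance is low. These are exploratory item-level comparisons, and the primary endpoints and the confirmatory testing sequence are untouched.

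**What to change.** 1. In SAP 9.2.5.4, assign 0 to 2b, 3b and 4b whenever the parent question is answered No, and delete the fracture-reported condition. Leave recorded non-zero answers as they are. Setting every pre-fracture fracture-item value to 0 would go too far: women may enrol 3 to 24 months after a proximal femur fracture and can truthfully report days limited by it.
2. In the third LAD paragraph of SAP 10.5.4, name the item used as pre-fracture baseline.
3. In the last LAD paragraph, state which visits are modelled. Either remove the change at report of fracture from any model whose outcome includes the reporting visit, or model only the later visits.

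The cost is a few lines of SAP text and the matching code, with no new data. It should be settled before unblinding, because the choice determines which women are analysed.

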#### **9.2.6 Dates**

No imputation will be done on incomplete stop date of an adverse event or a concomitant medication unless specified otherwise. For the purposes of deriving time-to-event variable from adverse event data or identifying from which point forward the data collected should be excluded or censored for the per-protocol analysis because of subjects receiving incorrect investigational product or proscribed therapies, incomplete start dates of adverse events or concomitant medications will be imputed as follows. Partial dates will be listed as is on the listings.

**Table 3. Imputation Rules on Incomplete Start Date of Adverse Event or Concomitant Medication**

	Missing	Impute	Exception
Start Date	Day	01	Default to Study Day 1 Date if the event started in the same year and month as Study Day 1
	Day / Month	01JAN	Default to Study Day 1 Date if the event started in the same year as Study Day 1
	Month	JAN	Default to Study Day 1 if the event started in the same year as Study Day 1
	Day / Month / Year	First Dose Date	Use randomization date for subjects who did not receive investigational product

If a death date (ie, End of Study date) is incomplete and missing only the day field, it will be imputed as the first day of the month if the latest date from other data is before the month of the death. However, if the latest assessment date is during the same month as the death, the partial death date will be imputed using the latest assessment date.

For dates of last period for menopause, the imputation rules for partial date are as follows: if the day is missing, default to day 15; if both month and day are missing, default to July 1. If the imputed date is on or after the randomization date, default to randomization date minus 1. Missing years will not be imputed.

If the date on the PRO administration page is partially or completely missing, the date of SC IP administration (or vital sign collection if SC IP is missing during the the double-blind period or during the open-label period) at the corresponding visit with the same CPEVENT will be used. Because it is expected that all PRO questionnaires be completed on the same day, EQ-5D-5L, BPI worst pain and LAD will use the same assessment date and the same imputation algorithm as that for OPAQ-SV.

### 9.2.7 Lab Parameters

Lab parameters with value below the lower limit of quantification (LLOQ) or above the upper limit of quantification (ULOQ) will be imputed as the LLOQ or ULOQ value, respectively.

### 9.2.8 Height

Missing post-baseline heights will be imputed using LOCF approach (by carrying forward the last nonmissing post-baseline value prior to the missing value). For the open-label period endpoints, only the open-label period value will be used for imputation, the values

in the double-blind period will not be carried forward into open-label period. The LOCF imputation will be done up to Month 24.

### **9.2.9 Oral IP Alendronate**

Boxes containing oral IP alendronate/placebo are dispensed to subjects every 2 months during the double-blinded period and oral IP alendronate are dispensed every 6 months during the open-label period. The number of tablets returned are collected in eCRF. Before the datasnapshot, these data will be cleaned. If the number of returned alendronate were missing, it will be imputed that subjects did not take any IP.

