**Non Amgen Investigational Product Dosage and Administration:**

During the 12-month double-blind ALN controlled study period, the ALN treatment group will receive 70 mg ALN PO QW and matched placebo for 210 mg romosozumab SC QM in a blinded fashion.

Following the 12-month double-blind ALN controlled study period, the ALN treatment group will receive open-label 70 mg ALN PO QW while remaining blinded to their initial treatment assignment (ALN).

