#### 6.1.1 Romosozumab/Placebo Dosage, Administration, and Schedule

During the 12-month double-blind ALN-controlled study period, subjects will receive 3 SC injections of romosozumab (ie, 3 injections of 70 mg romosozumab for a total dose of 210 mg) or matched placebo at each IP dosing visit (ie, Day 1 study visit and monthly study visits thereafter to Month 11). A separate PFS will be used for each injection; however, all 3 PFS to be used at a specific visit will be supplied in a single box, as assigned by the IVRS.

Injections will be administered by a healthcare professional into different sites on the subject's anterior abdominal wall, upper thigh, or upper arm. The injection should not be administered in the same arm from which blood is drawn. The romosozumab/placebo SC injection must be administered as the last procedure after all other study visit procedures have been completed. A physician must be available during administration of romosozumab/placebo. It is recommended that all subjects be closely observed for approximately 30 minutes after dosing with investigational product (IP).

The first dose of romosozumab/placebo should be administered on the day of randomization. If this is not possible, it must be administered within 72 hours of randomization.

Refer to specific instructions provided by the IVRS vendor for additional information on box assignment and to the IPIM for additional information regarding storage and preparation of IP.

Overdose with this product has not been reported. Neither the effects of overdose of romosozumab nor an antidote to overdose are known. The maximum amount of romosozumab that can be safely administered in a single dose has not been determined, and there is currently insufficient information to draw any conclusions about the safety of doses higher than those studied in clinical trials. The highest single dose of romosozumab tested in clinical trials is 10 mg/kg SC. Subjects who have received higher than protocol-defined doses should be carefully monitored for adverse events.

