**10.1.6.3 Per-protocol Analysis Set**

The per-protocol analysis set will only be used to analyze the following endpoints: subject incidence of clinical fracture, new vertebral fracture through Month 24, and nonvertebral fracture as sensitivity analyses for the primary analysis period and nonvertebral fracture for the overall study period. The per-protocol analysis set includes

subjects who are defined in [Section 10.1.6.1](#) (for new vertebral fractures in the primary analysis period) or [Section 10.1.6.2](#) (for clinical fracture and nonvertebral fracture in the primary or overall **study** analysis period) and receive the active investigational product with no major protocol violations in the corresponding analysis period. The major protocol violations will be defined in the Statistical Analysis Plan (SAP), and will be identified prior to study unblinding. Subjects in the per-protocol set will be analyzed according to their randomized treatment assignments.

**10.1.6.4 Primary Efficacy Analysis Set for BMD, Height, and PRO/ClinRO Endpoints for the Double-blind ALN-controlled Study Period and Primary Analysis Period**

This analysis set includes all randomized subjects who have a baseline and  $\geq 1$  post baseline evaluation at or before the time point under consideration. The efficacy analysis set may vary for different endpoints due to missing data. Subjects in the analysis set will be analyzed according to their randomized treatment assignments, regardless of treatment received.

**10.1.6.5 Safety Analysis Set for the Double-blind ALN-controlled Study Period, Primary Analysis Period, and Overall Study Period**

The safety analysis set includes all randomized subjects who receive  $\geq 1$  dose of investigational product in the 12-month of double-blind ALN-controlled study period. These subjects will be analyzed according to their actual treatment received, where subjects who received  $\geq 1$  dose of romosozumab will be analyzed in the romosozumab treatment group regardless of the randomized treatment.

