## **6. Definitions**

### **6.1 Basic Definitions**

#### **Investigational Product (IP)**

Romosozumab, ALN and the respective matched placebo

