#### First Dose Date

The date of administration of first dose of investigational product (ie, the first date recorded on the Investigational Product Administration eCRF for romosozumab or placebo with volume > 0 or the first dose date of ALN or placebo in

Alendronate/Placebo Dispensation eCRF with the number of tablets taken > 0, whichever is earlier), which may or may not be the same as the randomization date

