## **7.5 Safety Analysis Set**

This safety analysis set includes all randomized subjects who receive  $\geq 1$  active dose of investigational product in the 12-month double-blind ALN-controlled study period. This analysis set will be used to analyze safety data for the double-blind study period, primary analysis period, and overall study period. AEs that begin on the end of double-blind period date will not be included in the 12-month double-blind study period. AEs that begin on the date of the end of primary analysis study period will be included in the primary analysis study period. These subjects will be analyzed according to their actual treatment received, where subjects who received  $\geq 1$  dose of romosozumab will be analyzed in the romosozumab treatment group regardless of the randomized treatment. The subject incidence rates for the primary analysis study period include all events that occurred in the double-blind study period and all events occurred on and before the end of primary analysis date for those subjects who received at least one dose of open-label ALN.

If the study continues to the final analysis, the subject incidence rates for the overall study period include all events that occurred in the double-blind study period and all events occurred in the open-label ALN period for those subjects who received at least one dose of open-label ALN.

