## 10.6 Safety Analyses

Safety data will be summarized for subjects who received  $\geq 1$  dose of active investigational product by the actual treatment received in the double-blind period (any subject randomized to ALN arm who incorrectly receives  $\geq 1$  dose of romosozumab will be analyzed as receiving romosozumab).

Safety data for the double-blind period and for primary analysis period will be summarized separately using analysis set defined in [Section 7.5](#). Safety data will also be summarized for the overall study period (at final analysis) using analysis set defined in [Section 7.5](#).

**A listing of adverse events will be prepared for subjects who did not received any active dose of investigational product in the 12-month of double-blind period. A listing of adverse events occurring after double-blind period will be prepared for subjects**

who received at least one **active** dose of investigational product in the 12-month of double-blind period, remained on study in the open-label period without open-label alendronate exposure.

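### As the SAP is worded, an alendronate-arm woman with no returned-tablet count has no active dose and leaves the safety set, while a romosozumab-arm woman with the same course stays in

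*SAP*

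**What the plan says.** - **Missing counts.** SAP 9.2.9, which covers both the double-blind and the open-label period, states: "If the number of returned alendronate were missing, it will be imputed that subjects did not take any IP". It makes no exception for death, loss to follow-up or an unreturned pack.
- **Recognising an oral dose.** The First Dose Date definition in SAP 6.1.2 takes an oral date from the dispensation form only "with the number of tablets taken > 0". SAP 6.2 counts a woman as exposed when her summed dose is above zero.
- **Safety set in the SAP.** SAP 7.5 requires at least one "active dose of investigational product in the 12-month double-blind ALN-controlled study period". For women outside it, SAP 10.6 says: "A listing of adverse events will be prepared for subjects who did not received any active dose of investigational product".
- **Safety set in the protocol.** Protocol 10.1.6.5 requires at least one "dose of investigational product in the 12-month of double-blind ALN-controlled study period", without the word *active*. SAP 6.1 defines investigational product (IP) as "Romosozumab, ALN and the respective matched placebo", so a placebo injection is a dose of IP.
- **Treatment.** According to the protocol synopsis, in the double-blind period "the ALN treatment group will receive 70 mg ALN PO QW and matched placebo for 210 mg romosozumab SC QM". Injections are given in clinic: "Injections will be administered by a healthcare professional into different sites" (Protocol 6.1.1). Tablets are self-administered from a two-month supply, first counted at Month 2 (Protocol 6.2.1).

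**The concern.** Membership of a safety set should not depend on arm and early outcome together. Here the evidence of an active dose is a clinic record in one arm and a returned-pack count in the other, and a missing count is read as proof that nothing was taken. For a woman known to have been dispensed drug, zero is an extreme value, and the SAP gives no reason for choosing it.

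At stake are the 12-month adverse event rates and the adjudicated deaths and cardiovascular events, which SAP 10.6.3 reports as incidence rates and odds ratios with confidence intervals. Those events may be few, so losing one or two from a single arm can show.

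**Working it through.** The plan gives no figure for this point, so there is none to reproduce. The main check is of the text; the arithmetic only sets the scale.

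**1. Two women with the same course.** Each is randomized, injected and dispensed tablets on Day 1, then dies or is lost before any return count is recorded.

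| Step | ALN arm | Romosozumab arm |
|---|---|---|
| Day 1 injection | placebo, recorded | romosozumab, recorded |
| Tablets dispensed | ALN | placebo |
| Tablets taken under 9.2.9 | 0 | 0 |
| Active doses | 0 | 1 |
| Safety set under SAP 7.5 | out, events listed only | in |
| Safety set under Protocol 10.1.6.5 | in, through the placebo injection | in |

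**2. Consistency of the safety set.** SAP 7.5 and 10.6 require an active dose. Protocol 10.1.6.5, SAP 10.6.1 (adverse events) and SAP 10.6.9 (abnormal laboratory values) require one dose of IP of any kind. SAP Section 11 declares a single change from the protocol, on a pain-score covariate. The move to active doses is therefore undeclared, and the SAP contradicts itself.

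**3. Number affected.** Inputs: 10% first-year dropout (Protocol 3.3 and 10.2), taken at a constant rate; 2,000 women per arm; first scheduled count at Month 2.

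- Share gone before Month 2: 1 − 0.90^(2/12) = 1.74%.
- Per arm: 2,000 × 0.0174 = 34.8, about 35 women. If 10% is read as the yearly hazard, the figure is 33.1.
- The share of these with no count is not in the documents. Assumed values:

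| Assumed share with no count | ALN-arm women excluded | Romosozumab-arm women excluded by this rule |
|---|---|---|
| 10% | 3.5 | 0 |
| 25% | 8.7 | 0 |
| 50% | 17.4 | 0 |
| 100% | 34.8 | 0 |

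**4. Direction and size of the distortion (illustration).** Assume equal true risk, with 20 or 40 events per arm in the year. Remove some ALN-arm women and events, and compute the odds ratio of romosozumab to ALN, whose true value is 1.00.

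| ALN-arm women out | ALN-arm events lost | Odds ratio, 20 events per arm | Odds ratio, 40 events per arm |
|---|---|---|---|
| 9 | 1 | 1.05 | 1.02 |
| 17 | 3 | 1.17 | 1.07 |

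For example, with 20 events, 17 women out and 3 events lost: (20/1,980) / (17/1,966) = 1.17. At a constant rate only 20 × 2/12 = 3.3 or 40 × 2/12 = 6.7 events per arm fall in the first two months. Losing 3 of 20 is therefore near the ceiling, and losing 1 is the more ordinary case.

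**5. Open-label period.** SAP 7.5 and 10.6.1 count later events only for women with at least one open-label ALN dose. Supplies then last six months, so the same imputation could drop events in either arm.

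**The case against.** The strongest reply is that the SAP does not settle on exclusion. Section 9.2.9 never mentions the safety set, and 10.6.1 and 10.6.9 would keep these women in. That is right, and it is why the point is partly one of reconciliation. It does not remove the problem: 7.5 is the section that defines the set, and 10.6 repeats the active-dose condition.

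Four stronger readings are tempting, and the documents do not support them.

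- *Every ALN-arm woman who leaves early drops out.* Protocol 7.3.13 has early leavers complete the Month 12 procedures, which include collecting unused tablets, and any later pack showing use restores inclusion. The group that remains is mainly early deaths and women lost to follow-up.
- *Oral exposure is known only from returned tablets.* SAP 6.1.2 refers to a first oral dose date, a last blinded oral dose date and a first open-label dose date. Under Wrong Dose Date, however, it says oral ALN dosing dates are not collected, and it gives no rule for a date that conflicts with an imputed zero.
- *Romosozumab-arm women never leave the set.* One with no recorded injection is also outside it. The rule on missing counts alone does not remove them.
- *The rule undermines the per-protocol or main fracture results.* Per-protocol ALN violations come from recorded protocol deviations (SAP 7.3, 7.4), and the primary fracture sets follow randomized assignment (SAP 7.1, 7.2).

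It is also fair to say that the excluded events are listed, that no cardiovascular tests are planned, and that data cleaning may reduce missing counts. Cleaning cannot supply a count for a pack that was never returned, and listed events still leave the rates and odds ratios.

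**Conclusion.** The point holds as a narrow one. Following SAP 9.2.9, 6.1.2, 7.5 and 10.6 as written produces a safety exclusion that depends on arm and on early death or loss. The number is small: about 3 to 35 of 2,000 ALN-arm women and no romosozumab-arm women through this rule. It rests on the planned dropout at a constant rate and on an assumed 10% to 100% of early leavers having no count.

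A reader might infer that the rule flatters romosozumab. It does the reverse, because early events leave the ALN arm only. In the illustration the odds ratio moves from 1.00 to between 1.02 and 1.17, depending on assumed event numbers that the documents do not give.

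Whatever the number, the conflict over the safety denominator between SAP 7.5 and 10.6, SAP 10.6.1 and 10.6.9, and Protocol 10.1.6.5 needs resolving.

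**What to change.** 1. In SAP 7.5 and 10.6, define the safety set as at least one dose of any IP, as in Protocol 10.1.6.5. The Day 1 injection then keeps women of both arms in, and a missing tablet count no longer affects membership for anyone who was injected.
2. In SAP 9.2.9, treat a missing return count as missing, not zero. It should not override a recorded oral dose date or dispensation when deciding whether a woman received a dose. Apply the same rule to the open-label ALN dose condition in 7.5 and 10.6.1.
3. Base the exposure summaries in SAP 10.6.12 on observed counts, and show the number missing.

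There is no need to impute every unreturned pack as fully taken. That would be the opposite single imputation, and the first change makes it unnecessary for the safety set.

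The cost is SAP wording and derivation code, with no new data. The downside is that a few women who took no tablets may be counted as exposed.
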